##### 4.6.3.2 Erythropoiesis Stimulating Agents

For subjects randomized to roxadustat the use of ESAs is generally prohibited. Erythropoiesis stimulating agent rescue is restricted to no more than one cycle of use during the Treatment Period; the Investigator may initiate use of an approved EPO analogue if all of the following criteria are met:

- A subject's Hb level has not sufficiently responded to two or more dose increases or the maximum dose limit of the study drug has been reached; and
- The subject's Hb is  $<$  8.5 g/dL on two consecutive measurements (central lab) drawn at least five days apart; and
- Clinical judgment does not suggest iron deficiency or bleeding as a cause of lack of response or rapid decline in Hb; and
- Reducing the risk of alloimmunization in transplant eligible patients and/or reduction of other RBC transfusion-related risks is a goal

The subject is not allowed to be administered both the EPO analogue and roxadustat at the same time. Treatment with an EPO analogue should be started  $\geq$  3 days after the last dose of roxadustat, and should be stopped when Hb  $>$  9 g/dL or after 4-weeks, whichever comes first. If a subject requires longer than 4-weeks therapy due to inadequate response the Medical Monitor should be contacted. Study treatment should be resumed after the following intervals:

- Two days after stopping epoetin
- One week after stopping darbepoetin alfa
- Two weeks after stopping methoxy polyethylene glycol-epoetin beta (Mircera®)

If more than one cycle of EPO analogue rescue is required, the Investigator should permanently discontinue roxadustat. Use of EPO analogues will be recorded in the eCRF.

Inadvertent ESA administration or ESA administration by the hospital staff in Roxadustat subjects should not be counted as rescue unless above criteria are met; these subjects may be allowed to continue taking study medication, if considered safe by the Investigator or Medical Monitor.

For subjects randomized to epoetin alfa, the Investigator may initiate use of a different EPO analogue if clinically indicated. Use of the different EPO analogue will be recorded in the eCRF and will be considered rescue therapy.

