3.2 Rescue Therapy & Emergency Procedures

Red Blood Cell Transfusion (for all subjects):

For subjects in both treatment groups, red blood cell (RBC) transfusion is allowed if rapid correction of anemia is required to stabilize the subject's condition (e.g. acute hemorrhage) or the investigator is of the opinion that the blood transfusion is a medical necessity. Study treatment may continue during or after RBC transfusion administration.

ESA use:

For subjects randomized to roxadustat the use of ESAs is generally prohibited. ESA rescue is restricted to no more than one 4-week cycle of use during the Treatment Period; the Investigator may initiate use of an approved epoetin (EPO) analogue if all of the following criteria are met:

- A subject's hemoglobin level has not sufficiently responded to two or more dose increases or the maximum dose limit of the study drug has been reached; and
- The subject's hemoglobin is < 8.5 g/dL on two consecutive measurements (central lab) drawn at least five days apart; and
- Clinical judgment does not suggest iron deficiency or bleeding as a cause of lack of response or rapid decline in hemoglobin; and
- Reducing the risk of alloimmunization in transplant eligible patients and/or reduction of other RBC transfusion-related risks is a goal

The subject is not allowed to be administered both the EPO analogue and roxadustat at the same time. Treatment with an EPO analogue should be started ≥ 3 days after the last dose of roxadustat, and should be stopped when hemoglobin > 9 g/dL or after a 4-week cycle has been completed, whichever comes first. If a subject requires longer than 4-week therapy due to inadequate response, the Medical Monitor should be contacted. Study treatment should be resumed after the following intervals:

- Two days after stopping epoetin
- One week after stopping darbepoetin alfa
- Two weeks after stopping methoxy polyethylene glycol-epoetin beta (Mircera[®])

If more than one cycle of EPO analogue rescue is required, the Investigator should permanently discontinue roxadustat. Use of EPO analogues will be recorded in the eCRF. Roxadustat subject who receives an ESA inadvertently and does not meet the criteria above may be allowed to continue taking study medication, if considered safe by the Investigator or Medical Monitor.

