9 STUDY MEDICATION

9.1 Extent of Exposure

Exposure to study medication will be summarized by treatment group in terms of treatment duration in weeks, which is calculated using the following formula: (the last dose date of study medication taken - the first dose date of study medication taken +1)/7.

Total weekly study drug exposure is defined as the total prescribed dose (in mg and mg/kg for roxadustat and IU and IU/kg for ESAEPO) of study drug administered within the week (windowed by 7-day period from Day 1).

Duration of exposure, weekly exposure and total study drug exposure will be tabulated by treatment group for the safety population.

Per dose amount and dosing frequency will also be tabulated by treatment group for the safety population and PPS population.

Patient-Exposure-Year (PEY) is defined as Last Dose Date – First Dose Date + 1.

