12.1 Adverse Events

Adverse events will be coded using the latest MedDRA version. An AE (classified by preferred term) started during the Treatment Period will be considered a treatment-emergent adverse event (TEAE) if it was not present prior to the first dose of study medication, or it was present prior to the first dose of study medication but increased in severity during the Treatment Period up to 7 days after last dose of study drug or until the administration of another anemia drug (other than the randomized treatment). An AE that occurs more than 7 days after study medication or after the administration of another anemia drug (other than the randomized treatment) will not be counted as a TEAE.

The number and percentage of subjects reporting TEAEs in each treatment group will be tabulated by system organ class and preferred term; by system organ class, preferred term, and severity; and by system organ class, preferred term, and relationship to study medication. If more than one event occurs with the same preferred term for the same subject, the subject will be counted only once for that preferred term using the most severe and most related occurrence for the summarization by severity and by relationship to the study medication. The distribution of TEAEs by severity and relationship to study medication will be summarized by treatment group.

The incidence of common ($\geq 5\%$ of subjects in any treatment group) TEAEs, treatment-emergent serious AEs (TESAE), and AEs leading to discontinuation of study medication will be summarized by SOC, preferred term and treatment group, sorted in decreasing frequency for the test treatment. In addition, the incidence of death and fatal SAEs (i.e., events that caused death) will be summarized separately by treatment group, SOC and preferred term. Treatment emergent adverse events of interest will also be reported in terms of incidence rate per Patient Exposure Year (PEY).

Discontinuation of study medication due to worsening anemia based on hemoglobin value (lack of efficacy) will not be counted under AEs leading to discontinuation.

Listings will be presented of subjects with serious adverse events (SAEs), subjects with adverse events leading to discontinuation, and subjects who died.

Temporal profile of TEAEs of special interest may also be plotted by treatment group showing the subjects in the y-axis and time to these TEAEs in the x-axis (Appendix 8).

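### Per-exposure TEAE rates stop counting events at another anemia drug but count exposure to last dose, so they are understated for subjects who receive an ESA and stay on roxadustat

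*SAP*

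**What the plan says.** **Events.** SAP 12.1 counts an AE as treatment-emergent up to 7 days after the last dose or until another anemia drug is given. A separate sentence repeats the 7-day limit and adds that any event "after the administration of another anemia drug (other than the randomized treatment) will not be counted as a TEAE". Nothing says that counting resumes if the subject goes back on, or stays on, study drug.

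**Exposure.** SAP 9.1: "Patient-Exposure-Year (PEY) is defined as Last Dose Date – First Dose Date + 1". There is no stop at another anemia drug. SAP 12.1 reports TEAEs of interest as an incidence rate per PEY, in addition to the tables of numbers and percentages.

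**Who continues after an ESA.** SAP 3.2: "Roxadustat subject who receives an ESA inadvertently and does not meet the criteria above may be allowed to continue taking study medication". Protocol 4.6.3.2 extends this to ESA given by hospital staff: "these subjects may be allowed to continue taking study medication, if considered safe by the Investigator or Medical Monitor". After a rescue cycle, SAP 3.2 says: "Study treatment should be resumed after the following intervals". Protocol 9.7 does not treat ESA given in hospital as a deviation when roxadustat was not allowed or available there.

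**The other arm.** SAP 3.2 and Protocol 4.6.3.2 allow epoetin subjects a different EPO analogue. SAP 11.3.3.2 records ESA doses needed in that arm as a dose change of study drug.

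**The protocol's definition.** Protocol 9.4.4.1 ends TEAE counting 28 days after the ET/EOT visit and has no stop at another anemia drug.

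**The concern.** Numerator and denominator of the same rate end on different dates for a group of subjects whom the protocol expects to exist. In a roxadustat subject who receives an ESA and stays on drug, every later event is dropped and every later day of exposure is kept. The documents give no frequency for this group, but the rationale for Amendment 2 describes ESA use in hospitalized roxadustat subjects as common.

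The trigger also differs by arm. For a roxadustat subject any ESA is another anemia drug. For an epoetin subject only an ESA other than epoetin alfa is. In an open-label, active-controlled trial with safety in its primary objective, a dilution that can fall more heavily on the test arm should not be left in a between-arm comparison of event rates.

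**Working it through.** The documents state no AE rate, event count or exposure total, so there is no figure of the plan's own to reproduce. The check builds the rate from the definitions, with PEY expressed in years.

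**1. Direction, one affected subject.** Let E1 events occur in time T1 before the ESA and E2 in time T2 after it, on drug. The plan reports E1/(T1+T2). This never exceeds (E1+E2)/(T1+T2), nor E1/T1. No assumption about the event rate is needed.

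**2. Size, one affected subject.** With a constant event rate, reported/true = T1/(T1+T2).
- ESA at Week 26, last dose Week 104: 26/104 = 0.25.
- ESA at Week 52, last dose Week 104: 52/104 = 0.50.
- ESA at Week 20, last dose Week 100: 20/100 = 0.20.

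**3. Share of arm exposure without ascertainment.** Assumptions, none from the documents: first other-ESA use at constant hazard h per year, every recipient stays on drug, common duration T years. The share is 1 − (1 − e^(−hT))/(hT). For h = 0.15 and T = 1.5, hT = 0.225 and the share is 1 − 0.2015/0.225 = 10.45%.

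**4. Offset from the 7-day tail.** Subjects never cut contribute 7 days of countable events after last dose that are not in PEY. With a constant event rate this adds e^(−hT) × (7/365.25)/T to the reported/true ratio. For h = 0.15 and T = 1.5 that is 0.7985 × 0.01278 = 1.02%, leaving a net understatement of 10.45% − 1.02% = 9.43%.

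| h per year | T (years) | Exposure not ascertained | Net understatement after tail |
|---|---|---|---|
| 0.05 | 1.5 | 3.7% | 2.5% |
| 0.05 | 3 | 7.1% | 6.6% |
| 0.10 | 1.5 | 7.1% | 6.0% |
| 0.10 | 3 | 13.6% | 13.1% |
| 0.15 | 1.5 | 10.4% | 9.4% |
| 0.15 | 3 | 19.5% | 19.1% |
| 0.20 | 1.5 | 13.6% | 12.7% |
| 0.20 | 3 | 24.8% | 24.4% |

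**5. Second parametrization.** Let a share f of the arm be affected at a fraction u of its exposure. Without the tail, reported/true = 1 − f(1 − u). Over f = 5% to 30% and u = 25% to 75% (assumed) this runs from 0.775 to 0.988. With the tail and 52 weeks on drug it runs from 0.788 to 1.006. The tail cancels the loss when f = 7/(7 + (1 − u) × days on drug): 2.5%, 3.7% and 7.1% at 52 weeks, and 1.3%, 1.9% and 3.7% at 104 weeks, for u = 25%, 50% and 75%.

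**6. What one window does.** Assume 100 subjects, 2 years on drug and 0.50 events per year, with 20% given an ESA at 1 year and continuing. Ignoring the tail:
- As written: 90/200 = 0.45.
- Events counted throughout: 100/200 = 0.50.
- Exposure stopped at the ESA: 90/180 = 0.50.

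**The case against.** **The cut may have been meant only for the post-dose tail.** In its first mention it is paired with the 7-day limit, and Protocol 4.1.3 lets an ESA start three days after the last roxadustat dose, inside that tail. On that reading the loss disappears. The second sentence of SAP 12.1, however, excludes such events without tying the exclusion to the end of treatment. The tail-only meaning may be the intention, but it is not what the text says.

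**The size is assumed.** This stands. No ESA rate is given, continuation after inadvertent or hospital use is conditional, and a need for a second rescue cycle ends roxadustat. SAP 12.1 counts a subject once per preferred term in its tables. If the PEY rate follows that convention, later events in a subject who already had one cost nothing; the SAP does not say which convention applies.

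**Reach is limited.** This also stands. The per-PEY rate is an additional descriptive summary of TEAEs of interest. Deaths and fatal SAEs are summarized separately, and adjudicated cardiovascular events are analysed under pooled plans. A reader might infer that the cardiovascular safety conclusion is affected; the documents do not support that. The rate nevertheless remains a study-level output.

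**Two further inferences go too far.** One is that the epoetin arm escapes the cut: it does not, because a different EPO analogue triggers it there. The other is that the rule selectively discards high-risk time after hospitalization: no document gives risk by time since admission, and an event that caused the admission precedes the hospital ESA and is not removed by that dose.

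**Conclusion.** As written, the per-PEY rate of TEAEs of interest is understated for subjects who receive an ESA and then continue or resume roxadustat. For those subjects the direction follows from the definitions alone.

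For the roxadustat arm as a whole, the direction depends on how many are affected. The tail can offset the loss when the share is small (break-even 1.3% to 7.1% in the cases shown); above that the arm's rate is too low. With first other-ESA use at an assumed 0.05 to 0.20 per year, 1.5 to 3 years on drug, and all recipients continuing, about 4% to 25% of roxadustat exposure has no TEAE ascertainment, and the net understatement is about 2% to 24%. These are illustrations, not estimates for this trial.

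A tempting stronger reading is that the rule gives roxadustat a known advantage over epoetin. The documents support only that the rule can act unequally: they give no ESA-use rate for either arm, so the size of any imbalance cannot be derived. The point should be corrected before analysis, but it touches no confirmatory test.

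**What to change.** Make the change in SAP 12.1 and limit it to TEAE incidence rates. The PEY defined in SAP 9.1 also serves the hospitalization and missed-dialysis rates (SAP 11.3.2 and 11.3.3), whose numerators have no ESA cut; changing it there would create a new mismatch.

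State that one window, including the 7-day tail, applies to both events and exposure, and choose one of these:

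- Count TEAEs and exposure through last dose plus 7 days, regardless of other anemia drugs. This also returns post-ESA events to the tables of numbers and percentages, and is closer to the protocol's definition, which has no such cut.
- If the cut is kept, end TEAE exposure on the date the other anemia drug is first given, or at last dose plus 7 days if earlier. Post-ESA events then stay out of the tables, so add a sensitivity analysis under the first option.

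If the cut was meant only for the post-dose tail, reword the sentence to say so and align exposure in the tail. If any cut remains, define which products count as another anemia drug; iron and transfusion are unclear at present.

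The cost is a few words and one derived date, from ESA use already recorded in the CRF. Trial conduct and data collection do not change. Roxadustat rates may become slightly less favourable.

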12.2 Clinical Laboratory Parameters

Descriptive statistics for laboratory values (in US conventional and SI units) and changes from baseline at each assessment time point will be presented by treatment group for the following laboratory parameters collected in the study including but are not limited to the following:

- Hematology: Hemoglobin, hematocrit, RBC count, MCV, WBC count, WBC differential, and platelet counts, reticulocyte count;
- Chemistry: Alkaline phosphatase, ALT, AST, GGT, total bilirubin, LDH, lipase, total protein, albumin, fasting glucose, phosphate, uric acid, BUN, creatinine, sodium, and potassium;
- Serum iron, ferritin, TIBC, TSAT, reticulocyte hemoglobin content
- HbA1c
- Hepcidin, high-sensitivity C-reactive protein (hs-CRP)

Laboratory tests values are clinically significant (CS) if they meet either the low or high CS criteria (Appendix 6). The number and percentage of subjects with post-baseline CS values will be tabulated by treatment group. The percentages are to be calculated relative to the number of subjects with available non-CS baseline values and at least one post-baseline assessment. The numerator is the total number of subjects with at least one post-baseline CS value. In addition, shift tables will be presented by treatment group and time point. The following 3 data listings will be presented by subject:

- A listing of lab values for all lab tests at all collected time points.
- A listing of subjects with post-baseline CS values will be provided including the baseline and post-baseline values.
- A listing of all AEs for subjects with CS laboratory values will also be provided.

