9. Subject has a serum folate level  $\geq$  lower limit of normal (LLN) at screening

**Amendment 2:** Subjects with a serum folate level  $< LLN$  at screening may qualify upon receiving folate supplement (per local standard of care)

10. Subject has a serum vitamin B12 level  $\geq$  LLN at screening  
**Amendment 2:** Subjects with a Vitamin B12 level  $<$  LLN at screening may qualify upon receiving B12 supplement (per local standard of care)
11. Subject's alanine aminotransferase (ALT) and aspartate aminotransferase (AST) are  $\leq 3$  x upper limit of normal (ULN), and total bilirubin (TBL) is  $\leq 1.5$  x ULN at screening
12. Subject's body weight (dry weight in HD subjects) is 45.0 to 160.0 kg

**Only incident dialysis subjects who meet criteria 3.1, 5.1, and 6.1 (instead of criteria 3, 5, and 6) are allowed to participate under Protocol Amendment 2**

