12.3 Vital Signs

Blood pressures and heart rate baselines for predialysis are defined as the mean of values obtained from the last 6 weeks of screening including Day 1 prior to the first dose.

Descriptive statistics for vital signs (e.g., systolic and diastolic blood pressure, MAP, pulse rate, and respiratory rate) and their changes from baseline at each visit and at the end of study will be presented by treatment group.

Vital sign values are potentially clinically significant (PCS) if they meet both the observed value criteria and the change from baseline criteria listed in Table 8. The number and percentage of subjects with post-baseline PCS values will be tabulated by treatment group. The percentages are to be calculated relative to the number of subjects with baseline and at least one post-baseline assessment. The numerator is the total number of subjects with at least one post-baseline PCS vital sign value. Shift tables may be presented. A supportive listing of subjects with post-baseline PCS values will be provided including the subject ID, study center, baseline, and post-baseline values. A listing of all AEs for subjects with PCS vital signs will also be provided.

Table 8. Criteria for Potentially Clinically Significant Vital Signs

Vital Sign Parameter	Flag	Criteria*	
		Observed Value	Change from Baseline
Systolic Blood Pressure (mmHg)	High	≥ 170	Increase of ≥ 20
	Low	≤ 90	Decrease of ≥ 20

Diastolic Blood Pressure (mmHg)	High	≥ 100	Increase of ≥ 15
	Low	≤ 50	Decrease of ≥ 15
Pulse Rate (bpm)	High	≥ 120	Increase of ≥ 20
	Low	≤ 50	Decrease of ≥ 20
Weight (kg)	High	-	Increase of $\geq 10\%$
	Low	-	Decrease of $\geq 10\%$
*A post-baseline predialysis value is considered as a PCS value if it meets both criteria for observed value and change from predialysis baseline, respectively.			

Additional analyses include but are not limited to

- Subgroup analyses of subjects without any change in BP meds during Treatment Period
- Proportion of subjects meeting National Kidney Foundation BP target: within sBP 120-140 mmHg/dBP 70-90 mmHg at baseline, during treatment, and 4 weeks post treatment

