12.4 Electrocardiogram (ECG)

Descriptive statistics for ECG parameters (e.g., Heart Rate, PR interval, QRS interval, QT interval, and QTc interval) at baseline and changes from baseline at each assessment time point will be presented by treatment group. QTc interval will be calculated using both Bazett ($QTcB = QT / (RR)^{1/2}$) and Fridericia ($QTcF = QT / (RR)^{1/3}$) corrections; and if RR is not available, it will be replaced with 60/HR in the correction formula.

A plot for each parameter of mean (+/- 95% CI) versus visit will be produced by treatment group (roxadustat vs. Epoetin).

ECG parameters values are potentially clinically significant (PCS) if they meet or exceed the upper limit values listed in Table 9. The number and percentage of subjects with post-baseline PCS values will be tabulated by treatment group. The percentages are to be calculated relative to the number of subjects with available non-PCS baseline and at least one post-baseline assessment. The numerator is the total number of subjects with at least one post-baseline PCS ECG value. Shift tables may be presented. A listing for all subjects with post-baseline PCS value will be provided including the subject ID, study center, baseline, and post-baseline PCS values.

In addition, a listing of all TEAEs for subjects with PCS ECG values and a listing of subjects with post-baseline significant ECG abnormalities as reported by the investigators will also be provided.

Table 9. Criteria for Potentially Clinically Significant ECG

ECG Parameter	Unit	Higher Limit
QRS interval	Msec	≥ 150
PR interval	Msec	≥ 250
QTc interval	Msec	> 500 ; Change from baseline > 60

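### SAP 12.2 and 12.4 leave subjects abnormal at baseline out of the denominator but not the numerator, so as written the lab and ECG abnormality percentages are not proportions and can only err upward

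*SAP*

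**What the plan says.** SAP 12.2 (Clinical Laboratory Parameters) gives both halves of the percentage. The denominator: "The percentages are to be calculated relative to the number of subjects with available non-CS baseline values and at least one post-baseline assessment". The numerator, in the next sentence: "The numerator is the total number of subjects with at least one post-baseline CS value".

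SAP 12.4 (Electrocardiogram) repeats the pair. Percentages are taken "relative to the number of subjects with available non-PCS baseline and at least one post-baseline assessment", and "The numerator is the total number of subjects with at least one post-baseline PCS ECG value".

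SAP 12.3 (Vital Signs) has nearly the same numerator sentence but a different denominator: "The percentages are to be calculated relative to the number of subjects with baseline and at least one post-baseline assessment". Nobody is removed there for an abnormal baseline.

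The CS and PCS limits are in SAP Appendix 6 (labs) and SAP Table 9 (ECG). Protocol 9.4.4.2 and 9.4.4.4 promise counts and percentages of subjects with out-of-range post-baseline values but define no denominator. Lab shift tables are planned in SAP 12.2. ECG shift tables are optional in SAP 12.4, although Protocol 9.4.4.4 commits to them for the ECG interpretation.

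**The concern.** Excluding baseline-abnormal subjects from a denominator makes sense when the table is meant to show abnormalities that are new on treatment. The same subjects must then leave the numerator. Here they do not: someone already CS at baseline who has one further CS value adds one to the top and nothing to the bottom. A subject with no baseline but a later CS value does the same.

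The result is neither the rate of new abnormality among those at risk nor the prevalence of any post-baseline abnormality among all assessed. These are descriptive safety tables, and a reader would naturally take the percentage as the new-abnormality rate. At stake are the absolute rates reported for each arm and, to a lesser extent, the contrast between arms.

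**Working it through.** **Inputs.** The two definitions come from SAP 12.2 and 12.4. The documents state no CS or PCS rate, so there is no figure of the plan's own to reproduce. Let:

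- b = share of subjects CS/PCS at baseline (assumed 0 to 20%);
- q = chance that such a subject has at least one post-baseline CS/PCS value (assumed 0.5 to 1.0; one value suffices, and SAP 16.5.1 uses all post-baseline assessments for this purpose);
- p = the same chance for a subject not CS/PCS at baseline (assumed 5%).

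For simplicity, every subject has a baseline and a post-baseline assessment.

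**Formula.** Per subject randomized, the denominator is 1−b and the numerator as written is (1−b)p + bq. The ratio is

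[(1−b)p + bq] / (1−b) = p + q·b/(1−b).

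With the numerator limited to denominator subjects it is p. The excess, q·b/(1−b), is never negative.

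**Results, p = 5%:**

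| b | Excess, q = 0.5 to 1.0 (points) | Percentage as written | Matched |
|---|---|---|---|
| 0 | 0 | 5.0% | 5.0% |
| 1% | 0.5 to 1.0 | 5.5% to 6.0% | 5.0% |
| 5% | 2.6 to 5.3 | 7.6% to 10.3% | 5.0% |
| 10% | 5.6 to 11.1 | 10.6% to 16.1% | 5.0% |
| 20% | 12.5 to 25.0 | 17.5% to 30.0% | 5.0% |

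**In counts.** Take 300 per arm (the 600-subject minimum at 1:1), b = 10%, q = 0.8, p = 5%. The denominator is 270. The numerator is 270 × 0.05 + 30 × 0.8 = 13.5 + 24 = 37.5. As written: 37.5/270 = 13.9%. Matched: 13.5/270 = 5.0%. All subjects in both halves: 37.5/300 = 12.5%. The written rule gives neither coherent answer.

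**Between arms.** The same expected excess is added to each arm, so an absolute difference is preserved in expectation but a ratio shrinks. With b = 5% and q = 0.9 the excess is 0.9 × 0.05/0.95 = 4.7 points. True rates of 6% and 3% print as 10.7% and 7.7%, and the ratio falls from 2.0 to about 1.4. Chance imbalance adds noise: b of 12% against 10% at q = 0.8 gives 0.8 × (0.12/0.88 − 0.10/0.90) = 2.0 points.

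**Which parameters are exposed.**

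- Baseline abnormality causes no inflation for creatinine and BUN, whose limits in SAP Appendix 6 are multiples of the Day 1 value, or for the QTc criterion "Change from baseline > 60", which a baseline value cannot meet.
- Little is likely for ALT, AST and total bilirubin. Protocol 5.1, criterion 11 ("Subject's alanine aminotransferase (ALT) and aspartate aminotransferase (AST) are" at most 3 × ULN, bilirubin at most 1.5 × ULN at screening) nearly coincides with the CS limits of at least 3 × ULN and above 1.5 × ULN. A rise between screening and Day 1 remains possible.
- Exposed: ALP, GGT, calcium, potassium, sodium, total protein, platelets, neutrophils, WBC, QRS, PR, and QTc above 500 read as a criterion in its own right. The eligibility criteria set no ECG-interval limit.

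**The case against.** The best defence is that this is loose wording rather than an intended rule. The numerator sentence is almost identical in SAP 12.2, 12.3 and 12.4 and looks like a template. A percentage taken relative to a stated set of subjects can be read as counting within that set, and the table specifications sit in a separate document (SAP 1), where the restriction may be made. Inflation would then occur only if the text were programmed literally. This limits certainty about what will be printed, but it does not rescue the text. The numerator is called a total, and in 12.3 the same sentence goes with a denominator that excludes no one for an abnormal baseline, where it plainly means all subjects.

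The second defence is that lab shift tables and listings of subjects with CS or PCS values, showing baseline and post-baseline results, are already planned. They would let a careful reader detect the problem. They do not correct the percentage.

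The third is that the error is small or absent for several important parameters, similar in both arms in expectation, and upward, so it would not hide abnormal values. That stands and limits the consequence.

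A reader might also infer that baseline abnormality is so common in dialysis patients that it drowns any signal, or that any chance baseline imbalance will pass for a drug effect. The documents support neither. They give no baseline abnormality rate, and an imbalance of two percentage points moves the contrast by about two points under the assumptions above.

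**Conclusion.** The point holds. SAP 12.2 and 12.4 state a numerator and a denominator that do not match, and nothing else in either document restores the match. Followed as written, the percentage is p + q·b/(1−b) rather than p: too high, or correct only when no one enters the numerator from outside the denominator. Subjects with a missing baseline push it the same way.

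The size cannot be fixed from the documents. Under the assumed q of 0.5 to 1.0 it runs from nothing at b = 0, through about half a point to one point at b = 1%, to 5.6 to 11.1 points at b = 10%. It applies to the exposed parameters only. The main harm is to absolute rates, with some dilution of relative contrasts and some noise from baseline imbalance.

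A percentage above 100 is possible algebraically, but it should not be presented as a realistic outcome. With p = 5% and q = 1 it needs b above 0.95/1.95, about 49%, and nothing in the documents suggests that. No efficacy conclusion is touched.

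**What to change.** In SAP 12.2 and 12.4, state that the numerator is the number of subjects in the denominator (non-CS or non-PCS baseline and at least one post-baseline assessment) who have at least one post-baseline CS or PCS value. Keep baseline-abnormal subjects in the lab shift tables already planned, and make the ECG shift tables in 12.4 firm rather than optional, which also brings that section closer to Protocol 9.4.4.4. Check that the separate table specifications follow the same rule.

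The cost is a sentence in each section and the matching table programming. No additional data are needed.
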